14.2. Exploratory Analysis

The change in CRP, serum tryptase, and plasma cytokines will be summarized descriptively by treatment group in the ITT (Intention-To-Treat) population. A further exploratory endpoint of FSD201 plasma exposure will be performed by analyzing plasma samples.

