5.2. Secondary Objectives

- To evaluate the efficacy of FSD201 as compared to placebo on pain-related function, sleep interference, and global improvement;

- To assess safety and tolerability of FSD201 in subjects with chronic widespread musculoskeletal nociceptive pain;
- To evaluate the change in serum tryptase, IL-6 and IL-1beta serum biomarker levels.

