5.3.2. Key Secondary endpoints

Key secondary efficacy endpoints will include changes from baseline to Day 56 as measured by:

- Percentage of subjects achieving $\geq 30\%$ reduction in NPRS score at the end of treatment with FSD201¹
- Change in Patient Global Impression of Change (PGIC) after 56 days treatment
- Change or reduction in patient average daily NPRS after 56 days of treatment¹;
- Change in Patient-Reported Outcomes Measurement Information System (PROMIS) Sleep Disturbance- Short Form (SF) 8a after 56 days treatment
- Change in the PROMIS Pain Interference- SF 8a score after 56 days treatment
- Change in the PROMIS General Life Satisfaction- SF 5a after 56 days treatment
- Change in the PROMIS Fatigue- SF 8a after 56 days treatment
- To determine whether FSD201 treatment reduces serum mast cell tryptase, IL-6 and IL-1beta during treatment.

Key secondary efficacy endpoints will include changes from baseline to Day 28 and Day 56 as measured by:

- Percentage of subjects achieving $\geq 30\%$ reduction in NPRS score¹
- Change in Daily Sleep Interference Scale (DSIS) after 28 and 56 days of treatment¹
- Change in Patient Global Impression of Change (PGIC).

Note:

¹DSIS and NPRS averages will be calculated as follows:

Baseline: calculated weekly average from Day -7 to Day -1

Day 28: calculated weekly average from Day 22 to Day 28

Day 56: calculated weekly average from Day 49 to Day 55 for the NPRS and Day 50 to Day 56 for the DSIS

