5.3.4. Exploratory endpoints

- Changes in CRP, IL-2, IL-4, IL-8, IL-10, IL-12 (p70), IL-13, TNF- α and IFN- γ from baseline to Day 14, Day 28 and Day 56.
- FSD201 plasma exposure will be performed by analyzing plasma samples.
- Change or reduction in patient weekly PI-NRS after 28 and 56 days of treatment.

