13.2. Procedures for Expedited Reporting

Responsibility for Reporting Serious Adverse Events to Regulatory Authorities

Ozmosis Research Inc. will provide expedited reports SAEs to Intrinsik for submission to Health Canada and FDA according to applicable guidelines and regulations, i.e. events which are BOTH serious AND unexpected, AND which are thought to be related to protocol treatment (or for which a casual relationship with protocol treatment cannot be ruled out).

Reporting Serious Adverse Events to Local Ethics Boards

Ozmosis Research Inc. will notify all Investigators of all Serious Adverse Events that are reportable to regulatory authorities from this trial or from other clinical trials as reported to the Sponsor. This includes all serious events that are unexpected and related to protocol treatment. Investigators must notify their Research Ethics Board (REB) / Institutional Review Board (IRB) and file the report with their Investigator Site File. Documentation that serious adverse events (SAEs) have been reported to REB/IRB must be kept on file at Ozmosis Research Inc.

Documentation can be any of the following:

- Letter from REB/IRB acknowledging receipt
- Stamp from the REB/IRB, signed and dated by REB/IRB chair, acknowledging receipt
- Letter demonstrating the SAE was sent to the board

All expedited serious adverse events occurring within a centre should also be reported to local REB/IRB.

14. Statistical Methods and Planned Analyses

The intent-to-treat (ITT) population will consist of all randomized subjects. The safety population will include all randomized subjects who receive at least one dose of the study drug. The per-protocol population will consist of all subjects in the ITT population who have no major protocol deviations that would have a significant effect on the efficacy of the study treatment. The ITT

population will be the primary population for all efficacy analyses. All safety data will be summarized based on the safety population. The per-protocol population will be used as the population for sensitivity analyses of the primary and key secondary efficacy endpoints.

All efficacy and safety will be summarized descriptively.

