14.1. Efficacy Analysis

As the primary analysis, the change from baseline in the weekly average of the daily pain intensity measured by NPRS will be analyzed using the mixed model for repeated measure (MMRM) with the treatment as a factor, visit, the interaction between treatment and visit, and baseline as a covariate. The analysis of covariance (ANCOVA) will also be used as an additional analysis. The change in the weekly average of the daily sleep score on Daily Sleep Interference Score (DSIS) and the change in the NPRS score will be analyzed using the same methods for primary endpoint analysis. The percentage of subjects achieving $\geq 30\%$ and $\geq 50\%$ reduction in NPRS score at Day 28 and Day 56 will be analyzed using Fisher's exact test and the logistic regression model. The change in Patient Global Impression of Change (PGIC) and other continuous efficacy endpoints will be analyzed using ANCOVA.

No multiplicity adjustment will be used in this study. The missing data imputation methods and sensitivity analyses for primary and key secondary efficacy endpoints will be included in Statistical Analysis Plan (SAP).

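### Tryptase, IL-6 and IL-1beta are key secondary efficacy endpoints, but the only text naming their analysis is a descriptive summary under Exploratory Analysis, so no between-arm estimate is clearly prespecified

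*Combined protocol and SAP*

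**What the plan says.** The secondary objective in Section 5.2 is "To evaluate the change in serum tryptase, IL-6 and IL-1beta serum biomarker levels". Section 5.3.2 opens its first list with "Key secondary efficacy endpoints will include changes from baseline to Day 56 as measured by" and ends that list with "To determine whether FSD201 treatment reduces serum mast cell tryptase, IL-6 and IL-1beta during treatment". The synopsis has the same entry. The exploratory list in Section 5.3.4, which begins "Changes in CRP, IL-2, IL-4, IL-8, IL-10, IL-12 (p70), IL-13", leaves these three markers out.

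The analysis text then divides. Section 14.1 gives a general rule: "The change in Patient Global Impression of Change (PGIC) and other continuous efficacy endpoints will be analyzed using ANCOVA". Section 14.2, under the heading Exploratory Analysis, gives a specific one: "The change in CRP, serum tryptase, and plasma cytokines will be summarized descriptively by treatment group in the ITT (Intention-To-Treat) population". It names no model, contrast or interval. The introduction to Section 14 adds that "All efficacy and safety will be summarized descriptively", and Section 14.1 states that "No multiplicity adjustment will be used in this study".

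**The concern.** Whether the drug reduces a marker is a causal question, and the randomised placebo arm is there to answer it. The natural output is a difference or ratio between arms with its uncertainty. The only sentence that names these markers in the analysis section promises a summary of change in each arm.

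The endpoint tier also decides other rules. Section 14.4 applies LOCF, with BOCF as sensitivity analysis, to efficacy endpoints. The introduction to Section 14 assigns per-protocol sensitivity analyses to the primary and key secondary efficacy endpoints. Whether either rule reaches these markers depends on which section governs. Unless this is settled before unblinding, the choice between a model and a table could be made with results in view.

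The markers matter to the programme. Section 4.1 presents biomarkers as evidence of biological effect, such as target engagement, and uses this to justify including them.

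**Working it through.** There is no stated figure to reproduce. The check is a comparison of the text, followed by the precision that a between-arm analysis would have.

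**How each section classifies the markers**

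| Place | Treatment of tryptase, IL-6, IL-1beta |
|---|---|
| 5.2 | Secondary objective |
| 5.3.2 and synopsis | Key secondary efficacy endpoint |
| 5.3.4 | Not on the exploratory list |
| 11 (Efficacy) | No biomarkers mentioned |
| 12.1 (Biomarkers) | Cytokine sampling placed under Safety |
| 14.1 | Not named; covered by the ANCOVA rule if read literally |
| 14.2 | Tryptase named, cytokines as a class; exploratory and descriptive |

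The documents therefore file the same markers as efficacy, safety and exploratory. A programmer would ordinarily follow the specific text in 14.2 over the general text in 14.1.

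**Details left open**

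- Time point: the heading in 5.3.2 says Day 56, while the endpoint itself refers to the treatment period. Samples are scheduled at Visits 2, 4, 6 and 10 (Days 0, 14, 28 and 56).
- Baseline: 5.3.2 defines it for NPRS and DSIS only. Tryptase is measured at both Visit 1 and Visit 2, and exclusion criterion 25 in Section 10.3 removes patients above 13.2 µg/L.
- Matrix: 5.2 refers to serum biomarker levels, 14.2 to plasma cytokines.

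**Gain from baseline adjustment**

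Assume equal variance σ² at baseline and follow-up, with correlation r.

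- Change-score variance: 2σ²(1 − r).
- ANCOVA residual variance: σ²(1 − r²).
- Ratio: (1 − r²) / [2(1 − r)] = (1 + r)/2.
- r = 0.5 gives 0.75; r = 0.8 gives 0.90.

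The documents give no correlation, so this range is an assumption.

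**Precision with 40 versus 20** (Section 10.5; no dropout; two-sided 0.05 assumed, as the documents state no alpha)

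- Standard error in SD units: √(1/40 + 1/20) = √0.075 = 0.274.
- 95% CI half-width, unadjusted: 1.96 × 0.274 = 0.54 SD.
- The same after adjustment, in SDs of the change score: 0.537 × √0.75 = 0.46 at r = 0.5, and 0.537 × √0.90 = 0.51 at r = 0.8.
- Difference detectable with 80% power, unadjusted: (1.960 + 0.842) × 0.274 = 0.77 SD.
- Unadjusted power for true effects of 0.3, 0.5 and 0.8 SD: about 19%, 45% and 83%.
- Three independent tests at 0.05 with no true effect: 1 − 0.95³ = 14% chance of at least one false positive.

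**The case against.** The strongest reply is that the ANCOVA rule in 14.1 already covers these markers, because 5.3.2 lists them as efficacy endpoints. Descriptive text need not exclude a model here: the introduction to Section 14 says that all efficacy is summarised descriptively, yet the primary endpoint also gets an MMRM. Section 14.2 does not say that its summary is the sole analysis. This stands as a possible reading, so it cannot be asserted that no between-arm analysis is planned. It does not remove the problem, because 14.1 names none of the three markers and 14.2 does.

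A reader might infer that the question gets no answer against placebo at all. The documents do not support that. The summary in 14.2 is by randomised group, so the placebo change appears beside the drug change and carries the same time trend and regression to the mean. What is missing under 14.2 is a stated contrast and its uncertainty.

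A reader might also claim a larger precision gain, with adjustment leaving 1 − r², or 75% to 36% of the variance at r = 0.5 to 0.8. That compares ANCOVA with unadjusted follow-up values. Section 14.2 summarises change, so (1 + r)/2 is the relevant ratio. If the ANCOVA in 14.1 already applies, nothing is gained.

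Skewed cytokine values dominating the placebo mean is plausible but not shown. The documents give no distribution, 14.2 does not commit to raw means, and the tryptase exclusion limits the upper tail at entry.

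Finally, the trial is sized for a responder-based Go/No-Go decision, and the objective in 5.2 does not itself mention placebo. Both are fair reasons to treat biomarker results as supportive. Neither is a reason to leave out an estimate with its interval.

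**Conclusion.** The point holds as a conflict between 5.3.2 with 14.1 (key secondary efficacy, ANCOVA by the general rule) and 14.2 (exploratory, descriptive). Followed as the specific text, 14.2 leaves a key secondary question without a prespecified effect size or confidence interval. The conflict itself rests on the wording alone and needs no assumption.

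The size of the gain is moderate. Baseline adjustment would leave 75% to 90% of the variance of an unadjusted change-score comparison, if the correlation is 0.5 to 0.8 and the variances are equal. The larger benefit is that the contrast is fixed in advance. Precision would remain modest, with an unadjusted half-width of about 0.54 SD before any dropout, and there is no multiplicity control. Such results could support a mechanism but could not confirm one.

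**What to change.** Take tryptase, IL-6 and IL-1beta out of the descriptive sentence in 14.2 and name them in 14.1. Specify for each:

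- a baseline-adjusted comparison between arms, either ANCOVA at Day 56 or the MMRM used for the primary endpoint with Day 56 as the main contrast;
- preferably log-transformed values, with the FSD201/placebo geometric mean ratio and 95% CI, and a rule for values below the quantification limit;
- the Visit 2 value as baseline, with a statement that it is drawn before the first dose;
- one matrix term, serum or plasma, in 5.2, 5.3.2 and 14.2;
- whether the missing-data and per-protocol rules apply.

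Keep CRP and the other cytokines descriptive, align Sections 11 and 12.1 with the chosen tier, and label the results as supportive. One main contrast per marker avoids nine comparisons (three markers by three visits). If the sponsor in fact regards the three markers as exploratory, 5.2, 5.3.2 and the synopsis should say so openly.

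The cost is protocol or SAP wording and three extra models. The samples are already scheduled.

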14.3. Safety Analysis

The safety analysis population includes subjects who received at least 1 dose of study medication. Safety endpoints include adverse events, vital signs, and clinical laboratory data. Safety endpoints will be listed and/or summarized descriptively by treatment group.

All adverse events (AEs) will be coded using the most recent MedDRA Version. The incidence of TEAEs, SAEs, and AEs leading to treatment discontinuation will be summarized by system organ class and preferred term. Summaries in terms of severity and relationship to study drug will also be provided. SAEs will be summarized separately in a similar manner. Subject listings of AEs causing discontinuation of study medication and SAEs will be produced.

Clinical laboratory data and vital signs will be summarized, including absolute values and changes from baseline values and numbers of subjects with clinically significant values. The incidence and

severity of treatment-emergent changes in laboratory values will be summarized separately; Summary tables will be provided for physical examination by treatment group and visit where appropriate. Vital signs analysis will include the mean, standard deviation, minimum, maximum, and quartiles at baseline and at the end of treatment, and the change from baseline to the end of treatment. Concomitant medications will be analyzed descriptively.

14.4. Methods for Handling Missing Data

Reasonable efforts will be made to obtain complete data for all subjects; however, missing observations may occur due to subjects lost to follow-up or non-adherence to required assessments. The reasons for missing data will be evaluated. In addition, the distribution of prognostic factors between subjects with data and those without data will be examined to evaluate any potential sources of bias. In the absence of any apparent systematic loss, data will be analyzed assuming that these observations are missing at random.

For efficacy endpoints, missing data will be adjusted in the analysis by using the method of last observation carried forward (LOCF). A sensitivity analysis will be carried out using the baseline observation carried forward (BOCF).

15. Investigational Obligations

15.1. General considerations

The end date for the study overall will be defined as the date of last contact or final contact attempt for the last subject completing or withdrawing from the study. If the Sponsor were to suspend or terminate the study prematurely for any reason, prompt notification would be given to investigators, REBs, IRBs, and regulatory authorities in accordance with regulatory requirements.

The Sponsor should be notified promptly if the study is terminated by the investigator or the REB/IRB at the applicable study site. A particular study site may be terminated from this study at the discretion of the investigator, Sponsor, or REB/IRB (e.g., for nonenrolment of subjects or noncompliance with the protocol).

15.2. Ethical Guidelines for the Conduct of the Study

The investigator is responsible for ensuring that the study is conducted in accordance with the clinical protocol and is in full compliance with FDA regulatory requirements; the basic principles outlined in 21 CFR Parts 50, 54, 56 & 312, the ICH-Guidelines for Good Clinical Practice as published in the Federal Register on May 9, 1997, and the Declaration of Helsinki ([ICH 1996](#); [FDA Regulation 2021](#)).

15.3. Written Informed Consent

A written informed consent form will be provided to each subject describing this information. The investigator will inform the subject of the nature, risks, and purpose of the study. This form must

be reviewed and approved by the Sponsor and the REB/IRB before its use in the study. Each volunteer must sign and date this form prior to their participation in the study. A signed original consent form for each subject will be kept on file at the clinical site. A copy will also be given to the subject signing the form.

15.4. Confidentiality

The Principal Investigator at each site and designees, employees and agents involved with this study will comply with relevant provincial/state and federal laws relating to the confidentiality, privacy and security of the subject's health information. They will only create, maintain, use or disclose any data that is generated by this study or other information disclosed to the Principal Investigator or their employees or agents during the course of the study to the Sponsor, REB/IRB, Health Canada, FDA or other authorized recipients as appropriate for the execution, analysis, review and reporting of this study. Such information shall not be used for any other purposes and will remain confidential.

16. Study Management

16.1. Approval and Consent

16.1.1. Regulatory Guidelines

This study will be conducted in accordance with the accepted version of the Declaration of Helsinki and all relevant regulations as set forth in Parts 50, 56, 312, Subpart D, of Title 21 of the United States Code of Federal Regulations (CFR), in compliance with International Council for Harmonisation and GCP guidelines and according to the appropriate regulatory requirements in the countries where the study was conducted.

16.1.2. Research Ethics Board or Institutional Review Board/Independent Ethics Committee

Conduct of the study must be approved by an appropriately constituted REB or IRB/IEC. Approval is required for the study protocol, protocol amendments (if applicable), IB, informed consent form (ICFs), recruitment material and patient information sheets, and other patient-facing material.

16.1.3. Informed Consent

For each subject (or the patient's Legally Authorized Representative (LAR)), informed consent will be obtained before any protocol-related activities. As part of this procedure, the principal investigator (PI) or designee must explain the nature of the study, its purpose, procedures, expected duration, alternative therapy available, and the benefits and risks involved in study participation. The subject (or the subject's LAR) should be informed that he/she may withdraw from the study at any time, and the subject will receive all information that is required by local regulations and guidelines for International Council for Harmonisation. The PI will provide the sponsor or its representative with a copy of the REB or IRB/IEC-approved ICF before the start of the study.

16.1.4. Data Handling

Clinical data will be entered by site personnel on eCRFs for transmission to the sponsor. Data on eCRFs transmitted via the web-based data system must correspond to and be supported by source documentation maintained at the study site. All study forms and records transmitted to the sponsor must only include coded identifiers such that directly identifying personal information is not transmitted. The primary method of data transmittal is via the secure, internet-based electronic data capture (EDC) system maintained by eClinical Services. Access to the EDC system is available only to authorized users via the study's internet website, where a user unique assigned username and password are required for access.

Any changes made to data after collection will be made through the use of data clarification forms or queries in the EDC system. When all missing and/or incorrect data have been resolved, eCRFs will be considered complete.

16.1.5. Source Documents

Source documents are considered to be all information in original records and certified copies of original records of clinical findings, observations, data, or other activities in a clinical study necessary for the reconstruction and evaluation of the study. The investigator will provide direct access to source documents and/or source data in the facilitation of study-related monitoring, audits, review by REBs or IRB/IECs, and regulatory inspections.

The investigator/institution should maintain adequate and accurate source documents and study records that include all pertinent observations on each of the site's subjects. Source data should be attributable, legible, contemporaneous, original, accurate, and complete. Changes to source data should be traceable, not obscure the original entry, and be explained if necessary.

16.1.6. Record Retention

Study records and source documents must be preserved for at least 25 years after the completion or discontinuation of/withdrawal from the study, at least 2 years after the drug being studied has received its last approval for sale, or at least 2 years after the drug development has stopped, and in accordance with the applicable local privacy laws, whichever is the longer period.

The investigator agrees to comply with all applicable federal, state, and local laws and regulations relating to the privacy of patient health information, including, but not limited to, the Standards for Individually Identifiable Health Information, 45 CFR, Parts 160 and 164 (the Health Insurance Portability Accountability Act of 1996 Privacy Regulation). The investigator shall ensure that study subjects authorize the use and disclosure of protected health information in accordance with Health Insurance Portability Accountability Act (HIPAA) Privacy Regulation and in a form satisfactory to the sponsor.

16.1.7. Monitoring

The study will be monitored to ensure that it is conducted and documented properly according to the protocol, GCP, and all applicable regulatory requirements. Ozmosis Research Inc. will organize remote/on-site monitoring of this study to be conducted as per the Monitoring Plan.

As this trial is conducted under both a CTA with Health Canada and an IND with the United States' Food and Drug Administration, your site may be subject to an inspection by the Health Products and Food Branch Inspectorate or FDA. Other audits may be conducted by the study sponsor, Ozmosis Research Inc.

